**Table 2: Schedule of Assessments – Part B (Multiple Dose)**

Study Epoch	Screening	Treatment		Follow-up	
		Days 1, 8, 15 & 22 pre-dose	Days 1, 8, 15 & 22 dosing & post-dose	Safety Follow-up	Additional Follow-up
Study Day (Window)	-28 to -1	1, 8 (+1), 15 (+1) & 22 (+1) (≥7 days between doses)		29 (+3)	36 (±3)
Informed consent	X				
Inclusion/exclusion criteria	X	X			
Demographic data a	X				
Medical history	X	X b			
Body weight and height	X			X c	
Oral body temperature	X	X d	X	X	X
Blood pressure and pulse rate	X	X d	X e	X	X
SpO 2	X	X d	X e	X	X
Physical examination	X	X	X f	X f	X f
Pregnancy test g	X	Day 1 pre-dose only		X	
Follicle-stimulating hormone h	X				
12-lead ECG	X	X	X i	X	
HRCT	X j				
Spirometry k	X	X l	X l	X	X
Carbon monoxide diffusion capacity k	X	X d		X	X
Clinical chemistry and hematology	X	X		X	
Serology	X				
Urine drugs of abuse screen m	X				
[REDACTED]	■	■	■	■	■
Study treatment administration			X		
Adverse event recording		X	X	X	X
[REDACTED]					
Pharmacokinetic blood sampling		Days 1 & 22	Days 1 & 22 n		
[REDACTED]		■		■	■
[REDACTED]		■		■	■
[REDACTED]				■	■

Study Epoch	Screening	Treatment		Follow-up	
		Days 1, 8, 15 & 22 predose	Days 1, 8, 15 & 22 dosing & postdose	Safety Follow-up	Additional Follow-up
Study Procedures	Screening				
Study Day (Window)	-28 to -1	1, 8 (+1), 15 (+1) & 22 (+1) (≥7 days between doses)		29 (+3)	36 (±3)

Note, where multiple assessments are required at a single timepoint, the following order of procedures should be used: blood sampling, spirometry, other procedures (ECGs should be scheduled before vital signs measurements). See also footnote k.

Note, timing of safety and pharmacokinetic assessments may be changed based upon findings from previous cohorts.

Abbreviations: DLCO = carbon monoxide diffusion capacity; ECG = electrocardiogram; HRCT = high-resolution computed tomography; SpO2 = oxygen saturation.

a To include smoking history.

b Interim medical history.

c Height measured only at Screening.

d Within 60 minutes prior to dosing.

e 1 hour and 2 hours after completion of dose administration.

f Symptom-directed physical examination.

g In women of childbearing potential. Blood pregnancy test will be performed at Screening and Safety Follow-up; urine pregnancy test will be performed at Day 1. If the Day 1 pregnancy test is positive, dosing of that subject should not proceed. If there is doubt over the accuracy of a positive urine pregnancy test result, a blood pregnancy test must be obtained through the central laboratory to confirm the result. A local blood pregnancy test may also be performed if considered to be in the best interest of the subject (eg, travel planning). If the local test is negative and there are no other clinical findings suggestive of pregnancy, the subject may be dosed.

h In postmenopausal women (at least 12 months postcessation of menses without an alternative medical cause) only, to confirm postmenopausal status. Confirmation of postmenopausal status requires level >40 mIU/mL in addition to appropriate history (refer to Section 6.5).

i 2 hours after completion of dose administration.

j If the most recent historical HRCT was performed more than 12 months prior to the initiation of Screening OR if the HRCT performed within 12 months prior to the initiation of Screening is determined not to be of suitable quality by the central over-reader, the imaging study must be repeated during Screening. Any HRCT used to establish subject eligibility must undergo central interpretation.

k Spirometry should preferably be performed before DLCO at timepoints where both assessments are required, but if not feasible, the rationale should be documented in source records and the order of testing implemented on Day 1 should be used at every subsequent study visit.

l Completion of a minimum of 3, maximum of 6 forced expiratory maneuvers within 60 minutes predose. Preferably 3 but a minimum of 2 maneuvers as soon as feasible but within 15 minutes after completion of dose administration and at 30 ± 5 minutes, 60 ± 10 minutes, and 90 ± 15 minutes after completion of dose administration (up to a maximum of 16 forced expiratory maneuvers per day).

m Exclusionary only if positive for a drug or metabolite of a drug that has not been prescribed and that remains positive on repeat testing.

n Within 5 minutes after completion of dose administration and 10, 30, and 60 minutes after completion of dose administration, to assay for parent drug (TRK-250). PK sampling times are given as targets to be achieved within reasonable limits (eg, ±10%).

p To avoid artifacts in any subsequent spirometry or DLCO assessments,

r The Day 1 sample must be taken prior to administration of any study treatment. Although it is preferred that the Day 15 sample is taken predose, this is not mandatory.

3 ABBREVIATIONS

Abbreviations pertain to the SAP only (not the TFLs).

AE	adverse event
AUC _{0-tlast}	area under the concentration-time curve from time zero to the time of the last quantifiable concentration
C _{max}	maximum observed plasma concentration
BID	twice daily
DL _{CO}	carbon monoxide diffusion capacity
DMC	data monitoring committee
ECG	electrocardiogram
FEV ₁	Forced expiratory volume over 1 second
FVC	forced vital capacity
ICF	informed consent form
IPF	idiopathic pulmonary fibrosis
MedDRA	Medical Dictionary for Regulatory Activities
█	█
PK	pharmacokinetic
QTcB	QT interval corrected for heart rate using Bazett's method
QTcF	QT interval corrected for heart rate using Fridericia's method
SAP	Statistical Analysis Plan
SOC	system organ class
SPO ₂	Oxygen saturation
TEAE	treatment-emergent adverse event
TFLs	tables, figures, and listings
T _{max}	time of maximum observed concentration

5 STUDY OBJECTIVES AND ENDPOINTS

5.1 Primary

The primary objective of the study is to assess the safety and tolerability of single and multiple inhaled doses of TRK-250 in subjects with idiopathic pulmonary fibrosis (IPF).

5.2 Secondary

The secondary objective of the study is to assess the PK in blood following single and multiple inhaled doses of TRK-250 in subjects with IPF.

[REDACTED]

[figure not shown]
6 STUDY DESIGN

This will be a Phase I, double-blind, randomized, placebo-controlled study conducted in 2 parts, single and multiple inhaled dose, at multiple sites.

6.1 Part A

Part A will comprise a single-dose, single-period, sequential-cohort study. Potential subjects will be screened to assess their eligibility to enter the study within 28 days prior to study drug administration.

[figure not shown]
It is planned that 16 subjects will be studied in 4 cohorts (Cohorts A1 to A4), each consisting of 4 subjects. Following DMC review of the safety and tolerability data from the first 4 cohorts, up to 3 further optional cohorts (Cohorts A5 to A7) of at least 4 subjects may be added to Part A to evaluate additional doses or to further evaluate planned doses.

6.2 Part B

Part B will comprise a multiple-dose, single-period, sequential-cohort study. Potential subjects will be screened to assess their eligibility to enter the study within 28 days prior to initial study drug administration.

It is planned to study 18 subjects in 3 cohorts (Cohorts B1 to B3), each consisting of 6 subjects. Up to 3 further optional cohorts (Cohorts B4 to B6) of at least 6 subjects may be added to evaluate additional doses or to further evaluate planned doses.

7 TREATMENTS

The following is a list of the masked study treatment abbreviations and ordering that will be used in the Closed Report.

Part A:

Cohorts	Treatment Order on TFLs
Cohort A1	TRK-250 2 mg
Cohort A2	TRK-250 10 mg
Cohort A3	TRK-250 30 mg
Cohort A4	TRK-250 60 mg
Cohort A...	... mg
All Cohorts in part A	Part A Pooled placebo

Up to 3 further optional cohorts (Cohorts A5 to A7) of at least 4 subjects may be added to Part A to evaluate additional doses or to further evaluate planned doses.

Part B:

Cohorts	Treatment Order on TFLs
Cohort B1	TRK-250 10 mg weekly
Cohort B2	TRK-250 30 mg weekly
Cohort B3	TRK-250 60 mg weekly
Cohort B...	... mg
All Cohorts in part B	Part B Pooled placebo

Up to 3 further optional cohorts (Cohorts B4 to B6) of at least 6 subjects may be added to Part B to evaluate additional doses or to further evaluate planned doses.

8 SAMPLE SIZE JUSTIFICATION

No formal statistical assessment, in terms of sample size, has been conducted. However, the number of subjects in each part of the present study is common in early clinical pharmacology studies and is considered sufficient to achieve the objectives of the study.

9 DEFINITION OF ANALYSIS POPULATIONS

The **Safety Population** will include all subjects who received at least 1 dose of study treatment (TRK-250 or placebo) and have at least 1 postdose safety assessment.

The **Pharmacokinetic (PK) Population** will include all subjects who received at least 1 dose of TRK-250 and have evaluable PK data.

The **All Subjects Population** will consist of any subjects who signed informed consent and had study assessments recorded on the database as per the protocol.

10 STATISTICAL METHODOLOGY

10.1 General

Data listings will be provided for the All Subjects Population. Summary statistics and statistical analyses will be performed for subjects included in the relevant analysis populations

For continuous data, summary statistics will include the arithmetic mean, arithmetic standard deviation, median, minimum, maximum, and number. For log-normal data (eg, the PK parameters: areas under the concentration-time curve [AUCs] and maximum observed concentration [C_{max}]), the geometric mean and geometric coefficient of variation (CV%) will also be presented. For categorical data, frequency counts and percentages will be presented. Data listings will be provided for all subjects up to the point of withdrawal, with any subjects excluded from the relevant population highlighted. For the calculation of summary statistics and statistical analysis, unrounded data will be used.

Missing values will not be imputed.

Data analysis will be performed using SAS[®] Version 9.4 or greater.

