### 4.4. Subject Withdrawal and Replacement

A subject is free to withdraw from the study at any time. In addition, a subject will be withdrawn if any of the following criteria are met:

- change in compliance with any inclusion/exclusion criterion post randomization that is clinically relevant and affects subject safety as determined by the Investigator.
- noncompliance with the study restrictions that might affect subject safety or study assessments/objectives, as considered applicable by the Investigator.
- any clinically relevant sign or symptom that, in the opinion of the Investigator, warrants subject withdrawal.

If a subject is withdrawn, the Sponsor and [REDACTED] will be notified by the Investigator and the date and reason(s) for the withdrawal will be documented in the subject's Case Report Form (CRF). If a subject is withdrawn, efforts will be made to perform all follow-up assessments, including the Additional Follow-up visit assessments, if possible ([Appendix 5](#)). Other procedures may be performed at the Investigator's or Sponsor's discretion. If the subject is in-house, the Safety Follow-up procedures should be performed before the subject is discharged from the clinic, if possible. The Investigator may also request that the subject return for a separate follow-up visit to complete the Safety Follow-up procedures. Any withdrawn subject who completes the Safety Follow-up procedures should be invited to attend for a separate follow-up visit to complete the procedures scheduled for the Additional Follow-up visit; this additional visit should be performed approximately 1 week after the Safety Follow-up procedures. All withdrawn subjects will be followed until resolution of all their AE or until the unresolved AE are judged by the Investigator to have stabilized.

Subjects who are withdrawn for reasons not related to study drug, including randomized subjects who never receive study drug, may be replaced following discussion between the Investigator and the Sponsor to ensure the required number of subjects complete each cohort. Subjects withdrawn as a result of an AE thought to be related to the study drug will generally not be replaced.

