### **6.1.2. Prohibited Concomitant Therapies**

Taking pirfenidone and nintedanib simultaneously is prohibited for subjects enrolled in this study.

Taking a systemic corticosteroid, cytotoxic therapy (eg, chlorambucil, azathioprine, cyclophosphamide, or methotrexate), vasodilator therapy for pulmonary hypertension (eg, bosentan), unapproved treatment for IPF (eg, interferon-gamma, penicillamine, cyclosporine, mycophenolate, or N-acetylcysteine), or any other investigational treatment is prohibited for subjects enrolled in this study.

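### SAP 10.1 ends data listings at the point of withdrawal, although Protocol 4.4 asks for follow-up safety assessments after it

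*SAP*

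**What the plan says.** SAP 10.1 sets the listing rule: "Data listings will be provided for all subjects up to the point of withdrawal, with any subjects excluded from the relevant population highlighted". Summaries follow a separate rule in the same section: "Summary statistics and statistical analyses will be performed for subjects included in the relevant analysis populations". The Safety Population in SAP 9 "will include all subjects who received at least 1 dose of study treatment (TRK-250 or placebo) and have at least 1 postdose safety assessment", so a dosed subject who later withdraws normally stays in it.

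Protocol 4.4 treats withdrawal as an event that comes before further data collection: "If a subject is withdrawn, efforts will be made to perform all follow-up assessments, including the Additional Follow-up visit assessments, if possible". It adds: "All withdrawn subjects will be followed until resolution of all their AE or until the unresolved AE are judged by the Investigator to have stabilized". One of its withdrawal criteria is "any clinically relevant sign or symptom that, in the opinion of the Investigator, warrants subject withdrawal".

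SAP 10.6.1 lists all adverse events and gives those leading to withdrawal a listing of their own. SAP 10.6.2 to 10.6.7 plan summaries and individual listings for laboratory data, vital signs, ECG, SpO2, spirometry and DLCO. SAP 10.6.8 lists, without summarizing, any safety assessment that SAP 10.6 does not otherwise cover.

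**The concern.** The protocol plans to obtain safety measurements after withdrawal, and the SAP's general rule stops the listings before they occur. Possible intolerance is one reason for withdrawal, so part of what goes unlisted comes from subjects in whom a reviewer would want to see whether a change resolved.

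This is a first-in-human study with safety as its primary objective, very small dose groups and no inferential analysis (SAP 10.6.9). In that setting the individual listing is a main way of reading the data. If summaries include values that the listings omit, the tables cannot be traced back to individual records. An adverse event could also be listed without the measurements that show its course.

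**Working it through.** This is a comparison of texts. The plan gives no figure to reproduce beyond the design counts, which agree: 4 cohorts × 4 = 16 subjects in Part A, 3 cohorts × 6 = 18 in Part B, 34 in total.

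**1. What falls after the cut.** Postdose visit days come from Protocol Appendix 5.

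| Part | Visit days | Withdrawn after | Scheduled visits after the cut |
|---|---|---|---|
| A | 1, 2, 3, 7, 14 | Day 1 | 4 of 5 |
| A | | Day 2 | 3 of 5 |
| A | | Day 3 | 2 of 5 |
| B | 1, 8, 15, 22, 29, 36 | Day 1 | 5 of 6 |
| B | | Day 8 | 4 of 6 |
| B | | Day 22 | 2 of 6 |

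In Part B the remaining dosing visits would probably not take place. In every row, though, Protocol 4.4 asks for the two follow-up visits. Together these hold two sets of vital signs, SpO2, spirometry and DLCO, and one set of ECG, chemistry, hematology and body weight.

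**2. What the summaries retain.** SAP 10.6.2 to 10.6.7 summarize chemistry, hematology, vital signs, ECG, SpO2, spirometry and DLCO, and no withdrawal cut is stated for them. Body weight and physical examination have no subsection in SAP 10.6. On the visible text (SAP 10.6.8 contains a short redaction) they are listed only. SAP 10.2 summarizes body weight as a demographic variable, not as a postdose outcome. Protocol 2.2.1 names body weight as a primary safety endpoint, and Appendix 5 schedules it after dosing only at Safety Follow-up. For a subject withdrawn before that visit, the only postdose weight would appear in neither a listing nor a table.

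**3. Values that may also leave the summaries.** SAP 10.1.2 excludes unscheduled readings from all summaries. For data types other than vital signs and ECG, any result not taken at a scheduled timepoint is unscheduled. Protocol 4.4 moves the follow-up of withdrawn subjects off schedule: an in-house subject has the Safety Follow-up procedures before discharge, and the additional visit comes about 1 week later. Two illustrations, assuming that the Safety Follow-up procedures are done on the day of withdrawal:

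- Part A, withdrawn on Day 2: procedures on Day 2, additional visit about Day 2 + 7 = 9. The scheduled windows are Days 7 to 10 and 14 ± 3 = Days 11 to 17. The Day 2 procedures precede both windows, and the additional visit falls in the Safety Follow-up window.
- Part B, withdrawn on Day 8: procedures on Day 8, additional visit about Day 15. The scheduled windows are Days 29 to 32 and 36 ± 3 = Days 33 to 39. Neither set falls in a window.

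The SAP has no rule for mapping such visits. If they count as unscheduled, they leave the summaries under 10.1.2 and the listings under 10.1. The QTc outlier analysis in SAP 10.6.4 is an exception, because it includes unscheduled readings.

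**4. How often.** The documents give no withdrawal rate. With an assumed rate p, independent across 34 subjects, P(at least one) = 1 − (1 − p)^34 and the expected number is 34p.

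| Assumed p | P(at least one) | Expected number |
|---|---|---|
| 3% | 0.65 | 1.0 |
| 5% | 0.83 | 1.7 |
| 10% | 0.97 | 3.4 |
| 20% | over 0.99 | 6.8 |

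One active subject is 1/3 (33%) of a Part A dose group or 1/4 (25%) of a Part B dose group (Protocol 3.1.1 and 3.1.2).

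**The case against.** The strongest reply is that the specific sections override the general one. SAP 10.6.2 to 10.6.7 promise listings of the individual measurements with no mention of withdrawal, and SAP 10.6.1 lists all adverse events. The cut-off term is undefined and could mean the subject's last contact with the study. The sentence might be meant only to say that withdrawn subjects stay in the listings. Listing content is set out in separate shells (SAP 4) that are not available here.

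Part of this stands. Adverse events are covered if 10.6.1 is followed, and the shells may already list everything. But the measurement sections say that individuals are listed; they do not say until when, so they do not lift a time limit set in 10.1. Protocol 4.4 uses withdrawal for the event that precedes follow-up, which makes the last-contact reading the less natural one. At best the SAP is open to two readings on what its listings contain.

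A reader might also infer that subjects who take a prohibited therapy are withdrawn and then cut off. The documents do not say so. Protocol 6.1.2 states only that such a therapy "or any other investigational treatment is prohibited for subjects enrolled in this study" and names no withdrawal consequence. The criterion in 4.4, "noncompliance with the study restrictions that might affect subject safety or study assessments/objectives, as considered applicable by the Investigator", is conditional and left to the Investigator.

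**Conclusion.** The conflict between SAP 10.1 and Protocol 4.4 is real and should be resolved before database lock. Its reach is limited. Data up to withdrawal, including the triggering event, are kept; summaries are not cut; and all adverse events are to be listed. The loss is complete only for data that are listed and not summarized (postdose body weight and physical examination) and for early follow-up values if they are classed as unscheduled. For FEV1, FVC, SpO2, DLCO and laboratory values, what is lost is the traceable individual course after withdrawal.

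Three stronger readings are tempting and not supported:

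- That withdrawn subjects lose their most informative data, or that the safety results are biased as a whole. The cut is written for listings, which estimate nothing.
- That 33% or 25% of a dose group's data disappears. Those figures are one subject's share of the group, not a share of data lost.
- That the no-changes statement in SAP 12 is false. Protocol 8.3 asks for safety parameters to be listed and summarized but sets no rule for data after withdrawal.

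The conclusion assumes that the cut-off means the withdrawal event of Protocol 4.4 and that the unseen shells do not say otherwise. The frequency range rests on assumed rates, and post-withdrawal visits take place only where possible.

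**What to change.** Replace the sentence in SAP 10.1 with: *Data listings will include all data recorded to the subject's last assessment, including assessments after withdrawal, which will be flagged with the withdrawal date and reason.* Keep the highlighting of subjects excluded from a population. This wording removes the undefined cut-off.

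Add to SAP 10.1.2 that Safety and Additional Follow-up values of withdrawn subjects, including those obtained early, are mapped to the corresponding follow-up visit in the Safety Population summaries and are not treated as unscheduled.

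Reconcile SAP 10.1 with the listing statements in SAP 10.6 and with Protocol 4.4, and check the listing shells against the result.

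The cost is SAP wording and listing programming. The protocol already asks for these data, so no new collection is needed, and no sample-size figure changes.

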10.1.1 Definition of Baseline and Change from Baseline

Baseline for each parameter is defined as the last value measured prior to dosing, including repeat (vital signs and electrocardiograms [ECGs]) and unscheduled (clinical laboratory parameters) readings (see Section 10.1.2 for definitions of repeat and unscheduled readings). For vital signs taken in triplicate, baseline will be the median of the last 3 values taken prior to dosing. For ECGs taken in triplicate, baseline will be the mean of the last 3 values taken prior to dosing.

Mean change from baseline is the mean of all individual subjects' change from baseline values. Each individual change from baseline will be calculated by subtracting the individual subject's baseline value from the value at the timepoint. The individual subject's change from baseline values will be used to calculate the mean change from baseline using a SAS procedure such as Proc Univariate.

10.1.2 Repeat and Unscheduled Readings

Repeat readings occur when the original vital signs or ECG result requires confirmation. Repeat readings are labelled as 'Repeat' in the listings and replace the original readings in all summaries and changes from baseline presentations and calculations. Prior to dosing, all readings taken in addition to the original reading are defined as predose repeats. Postdose repeat readings are defined as readings collected within 15 minutes of the actual time of the original reading. Where results are taken in triplicate and repeated, the last 3 readings are used in all subsequent calculations.

With the exception of predose results described above, unscheduled readings for vital signs or ECGs are defined as readings collected >15 minutes from the actual time of the original reading. Where results are taken in triplicate, the original reading is defined as the first reading of the triplicate. All results not taken at a scheduled timepoint for other data types (eg, clinical laboratory parameters) are unscheduled. Unscheduled readings are labelled as 'Unscheduled' in the listings. Because unscheduled readings are not associated with any scheduled timepoint, they are excluded from all summaries (with the exception that they may be used as baseline, as stated in Section 10.1.1).

